## **11.8. Safety Analyses**

If appropriate, safety data will be summarized for the Phase 1 part and Phase 2 part of the study separately, and for all the 2 parts combined.

### **Adverse Events**

The verbatim terms used in the eCRF by investigators to identify adverse events will be coded using the Medical Dictionary for Regulatory Activities (MedDRA) version 15.1 or higher. All reported adverse events with onset during the treatment phase

(ie, treatment-emergent adverse events, and adverse events that have worsened since baseline) will be included in the analysis. For each adverse event, the percentage of subjects who experience at least 1 occurrence of the given event will be summarized by treatment group.

Summaries, listings, datasets, or subject narratives may be provided, as appropriate, for those subjects who die, who discontinue treatment due to an adverse event, or who experience a severe or a serious adverse event.

### **Clinical Laboratory Tests**

Laboratory data will be summarized by type of laboratory test. Reference ranges and markedly abnormal results (specified in the Statistical Analysis Plan) will be used in the summary of laboratory data. Descriptive statistics will be calculated for each laboratory analyte at baseline and at each scheduled time point. Changes from baseline results will be presented in pre- versus posttreatment cross-tabulations (with classes for below, within, and above normal ranges). A listing of subjects with any laboratory results outside the reference ranges will be provided. A listing of subjects with any markedly abnormal laboratory results will also be provided.

Parameters with predefined National Cancer Institute Common Terminology Criteria for Adverse Events (NCI-CTCAE) toxicity grades will be summarized. Change from baseline to the worst adverse event grade experienced by the subject during the study will be provided as shift tables.

### **Cardiac Monitoring**

An assessment of shortening fraction and/or left ventricular ejection fraction (LVEF) will be assessed during screening by echocardiogram.

$$\text{LVEF} = \frac{\text{left ventricular (LV) diastolic volume} - \text{LV systolic volume}}{\text{LV systolic volume}}$$

$$\text{Shortening Fraction} = \frac{\text{LV end diastolic diameter} - \text{LV end systolic diameter}}{\text{LV end diastolic diameter}}$$

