**Footnotes:**

- a) By parent/legal guardian and/or subject as required by local regulation. Informed consent/assent needs to be in place prior to first study-specific screening assessment but is not considered as a screening assessment.
- b) The End of Sequential Treatment Visit occurs at the end of the last sequential treatment cycle (or within 7 days thereafter).
- c) The End of Treatment Visit occurs 30 +/- 5 days after last dose of DACOGEN plus cytarabine or single agent DACOGEN as part of this study whichever is later in both Phase 1 and 2.
- d) Follow-up is to include recording of any late-occurring, potentially study drug-related adverse events, date(s) of any further treatment, drugs, and doses used and date of death, and should occur every 3 months for a maximum of 3 years after the last subject is enrolled or until 80% of patients are deceased, whichever occurs first. This is the assessment of long-term toxicity.
- e) To include date of initial diagnosis, prior treatments, dates of prior treatments, response, and response duration
- f) DACOGEN is administered on Days 1-5 at 20 mg/m^2 per day and cytarabine on Days 8-12 at the protocol defined dose.
- g) Complete physical during screening (including vital signs ie, temperature, blood pressure, and pulse/heart rate) and at end of treatment. Limited examination focused on signs and symptoms at other times. Performance status (Karnofsky or Lansky) is evaluated prior to start of each cycle.
- h) Height prior to Cycle 1 and weight prior to each cycle to determine body surface area
- i) Safety assessment at each visit during treatment to include signs and symptoms of disease, adverse events, and any other changes in condition noted.
- j) Fractional shortening ≥ lower limit of normal (29%) or LVEF (>58%) by echocardiogram (preferred). Results obtained more than 14 days prior to enrollment are acceptable provided no potentially cardiotoxic medications were administered between that evaluation and Cycle 1 Day 1.

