## 6. Inclusion criterion has been modified:

6.1 Criterion modified per Amendment INT-1

6.2 Criterion modified per Amendment INT-2

Subject must have adequate organ function, defined as:

- Normal renal function defined as a creatinine clearance of at least 90 mL/min/1.73 m^2 as determined using the Schwartz equation. Glomerular Filtration Rate (ml/min/1.73 m^2) = k\*Height(cm)/serum creatinine (mg/dL) where k is a proportionality constant which varies with age and is a function of urinary creatinine excretion per unit of body size; k is 0.45 for children up to 12 months of age, 0.55 for older children and adolescent girls and 0.70 for adolescent boys (adolescent is referring to 12 to 18 years of age).
- Alanine aminotransferase (ALT)  $\leq 5 \times$  upper limit of normal (ULN) and total bilirubin less than  $1.5 \times$  ULN. If ALT is transiently elevated and clearly related to recent prophylactic intrathecal treatment since start of screening but prior to the first dose of decitabine, it should be discussed with the sponsor's medical monitor whether the dose can be started or should be postponed.
- Cardiac function must be normal, defined as shortening fraction of  $\geq 29\%$  by echocardiogram, or left ventricular ejection fraction (LVEF)  $> 58\%$ . Results obtained prior the screening period are acceptable provided no potentially cardiotoxic medication was administered between that evaluation and the first dose of decitabine (Cycle 1 Day 1).

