### 9.1.2. Screening Phase

The signed ICF/assent must be obtained before any study-specific procedures are performed. The Screening Phase begins when the first study-specific screening assessment is conducted. During the Screening Phase, eligibility criteria will be reviewed and a complete clinical evaluation will be performed. Screening procedures will be performed up to 14 days before Cycle 1 Day 1; however, results of tests such as radiologic tests, bone marrow collection for morphology, cytogenetics, and either immunohistochemistry or immunofluorescence performed up to 28 days before Cycle 1 Day 1 as routine work-up for the subject's disease can be used. Cardiac function must be normal, defined as shortening fraction of  $\geq 29\%$  by echocardiogram or LVEF  $> 58\%$ . Results obtained prior the screening period are acceptable provided no potentially cardiotoxic therapy was provided between that evaluation and the first dose of decitabine (Cycle 1 day 1). A negative pregnancy test for females of childbearing potential must be documented within 7 days before the Cycle 1 Day 1 dosing. If a pregnancy test result is more than 7 days old at Cycle 1 Day 1, then the test must be repeated locally and documented.

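### The LVEF formula in section 11.8 divides by systolic instead of diastolic volume, so it is not on the scale of the LVEF >58% entry threshold

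*Combined protocol and SAP*

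**What the plan says.** Section 11.8, under Cardiac Monitoring, states that shortening fraction and/or LVEF is assessed by echocardiogram at screening, and gives a formula for each.

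- **LVEF.** In the equation's markup, where the part after the inner pair of braces is the denominator: "left ventricular (LV) diastolic volume} - \text{LV systolic volume}}{\text{LV systolic volume". The difference between diastolic and systolic volume is divided by the systolic volume.
- **Shortening fraction.** "LV end diastolic diameter} - \text{LV end systolic diameter}}{\text{LV end diastolic diameter". The difference in diameters is divided by the end-diastolic diameter.

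The entry threshold appears in three places. Footnote j of the Time and Events Schedule has "Fractional shortening ≥ lower limit of normal (29%) or LVEF (>58%) by echocardiogram (preferred". Inclusion criterion 6 in section 4.1 begins "Cardiac function must be normal, defined as shortening fraction of" and goes on to at least 29%, or an LVEF above 58%. Section 9.1.2 repeats this. In all three places the two measures are joined by *or*, so either one is enough. Sections 4.1 and 9.1.2 and footnote j also accept results from before the screening window if no potentially cardiotoxic treatment was given in between.

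No other section defines LVEF or explains a systolic denominator.

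**The concern.** Both formulas are meant to express how much of the filled ventricle is lost in contraction. The shortening-fraction formula does so because it divides by the diastolic dimension. The LVEF formula divides by what is left after contraction, which gives a ratio of ejected to residual volume. That ratio is not a fraction of anything and can exceed 100%.

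The threshold of 58% is described as normal cardiac function and is paired with a shortening fraction of 29%. If LVEF were computed as section 11.8 prescribes, values well below a true 58% would clear the threshold. Because of the *or*, LVEF alone could then qualify a child whose shortening fraction was below 29% or not recorded. Any LVEF tabulated from volumes by this formula would also not be comparable with values taken from echocardiogram reports.

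**Working it through.** The documents contain no worked LVEF value to reproduce, so the check is algebraic.

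**Inputs.** Both formulas come from section 11.8. The thresholds (LVEF >58%, shortening fraction ≥29%) come from section 4.1 criterion 6, section 9.1.2 and footnote j. Write EDV and ESV for diastolic and systolic volume.

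**Relation between the two versions**

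- Printed: R = (EDV − ESV)/ESV
- Diastolic denominator: EF = (EDV − ESV)/EDV
- Since ESV = EDV × (1 − EF), R = EF/(1 − EF), and in reverse EF = R/(1 + R).

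R exceeds 100% whenever ESV is less than half of EDV.

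**Numbers**

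| True EF | Printed formula |
|---|---|
| 36.7% | 58.0% |
| 40% | 0.40/0.60 = 66.7% |
| 50% | 0.50/0.50 = 100% |
| 58% | 0.58/0.42 = 138.1% |
| 60% | 0.60/0.40 = 150% |
| 70% | 0.70/0.30 = 233% |

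The true EF at which the printed formula reaches the threshold is 0.58/1.58 = 36.7%.

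An example with EDV = 100 mL:

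- ESV = 42 mL: true EF 58/100 = 58.0%; printed 58/42 = 138.1%.
- ESV = 60 mL: true EF 40/100 = 40.0%; printed 40/60 = 66.7%, which passes >58%.
- ESV = 63.3 mL: true EF 36.7/100 = 36.7%; printed 36.7/63.3 = 58.0%.

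**Which denominator fits the paired 29% threshold?** This step needs an assumption that is not in the documents: LV volume is proportional to diameter to the power k, with k between 2 and 3. A shortening fraction s then gives EF = 1 − (1 − s)^k.

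| | k = 2 | k = 2.5 | k = 3 |
|---|---|---|---|
| LVEF matching a shortening fraction of 29%, diastolic denominator: 1 − 0.71^k | 49.6% | 57.5% | 64.2% |
| Shortening fraction matching LVEF 58%, diastolic denominator: 1 − 0.42^(1/k) | 35.2% | 29.3% | 25.1% |
| Shortening fraction matching LVEF 58%, printed formula: 1 − (1/1.58)^(1/k) | 20.4% | 16.7% | 14.1% |

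With a diastolic denominator, 58% corresponds to shortening fractions that bracket 29%. With the printed denominator it corresponds to values well below 29% across the whole range. The two entry thresholds agree in size only if LVEF has the diastolic denominator.

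**The case against.** The strongest objection is that nothing in the plan uses the formula. The eligibility text states the threshold directly and does not refer to section 11.8. No section asks sites to calculate LVEF by hand, earlier results are accepted, and no LVEF summary or endpoint is specified. The Time and Events Schedule appears to carry a second cardiac assessment after screening (the table is broken in the text available), but section 11.8 plans no analysis of it. Anyone who did use the formula would see values above 100% for every heart with a true EF above 50%, which would be conspicuous. On this view it is an editorial slip. The point about limited reach stands and keeps the size of the concern small. It does not make the definition right, and the Statistical Methods section is where a programmer would look for a derivation.

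Two further points also stand. First, the *or* narrows the affected group: a child with a documented shortening fraction of at least 29% qualifies whatever the LVEF. Second, the equation was machine-read from a PDF, and its denominator repeats the last term of the numerator, so a reading error is possible. Both formulas are complete and legible, so there is no sign of one, but the source page should be checked.

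It can also be said that the disagreement with 58% is one of scale, since the printed formula can give values on either side of 58%. That is correct. The cut-off simply no longer marks what the protocol calls normal function.

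**Conclusion.** The LVEF definition in section 11.8 is wrong as written and should be corrected. It differs from the adjacent shortening-fraction formula, is not bounded by 100%, and is not on the scale of the >58% threshold.

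The size is conditional. If LVEF is taken from the echocardiogram report, the effect is zero. If it is calculated from the printed formula, the threshold is met at any true EF above 36.7%. Eligibility could then differ only for a child with a true EF above 36.7% and up to 58% whose shortening fraction is below 29% or unavailable. The algebra needs no assumption beyond the usual meaning of an ejection fraction. The comparison with the 29% threshold rests on the assumed volume–diameter relation and is supporting evidence only. Response, dose-limiting toxicity and sample size are unaffected.

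**What to change.** Check the equation on the source page of section 11.8. If it reads as quoted, replace the denominator so that the definition becomes LVEF = (LV end-diastolic volume − LV end-systolic volume) / LV end-diastolic volume. This brings it into line with the shortening-fraction formula and with the scale of the threshold in section 4.1, section 9.1.2 and footnote j. The threshold itself does not change.

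The cost is one term in one definition, carried in the next formal amendment under section 17.1. It alters no threshold, endpoint, sample size or data collection. If any LVEF has already been derived from volumes with the printed formula, it can be converted exactly by EF = R/(1 + R).

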### **Vital Signs**

Descriptive statistics of temperature, pulse/heart rate, and blood pressure (systolic and diastolic) values and changes from baseline will be summarized at each scheduled time point. The percentage of subjects with values beyond clinically important limits will be summarized.

Descriptive statistics will be calculated at baseline and for observed values and changes from baseline at each scheduled time point. Frequency tabulations of the abnormalities will be made.

### **Physical Examination**

Physical examination findings will be summarized at each scheduled time point. Descriptive statistics will be calculated at baseline and for observed values and changes from baseline at each scheduled time point. Frequency tabulations of the abnormalities will be made.

## 11.9. Study Evaluation Team

A Study Evaluation Team (SET) will be established to review the safety data of the Phase 1 portion of the study to determine dose escalation, dose de-escalation, and the MTD of cytarabine.

The SET consists of the sponsor's statistician and clinician (one of whom will chair the committee) and other members as needed, eg, clinical pharmacologist, safety physician. The SET will also include the lead investigator or designee from each country where the study is being conducted. The SET will convene regularly during the Phase 1 portion of this study to assess DLTs, determine dose escalation or de-escalation, and whether a MTD has been reached for cytarabine under these study conditions. The SET may convene at additional times for data review or any safety-related issues including during Phase 2. Any SET member has the right to request a SET meeting. A medical consultant may be asked to participate in the SET if deemed necessary in the interest of patient safety, upon request from the Sponsor or the investigator in preparation for SET meetings. Decisions on dose escalations or de-escalations, changes in the timing of PK or PD sampling, or other study conduct recommendations, will be made by the SET and documented.

All decisions made by the SET (eg, dose escalation/de-escalation, modification of the administration schedule or regimen) will be documented in a SET decision document and distributed to investigators. The IRB will be notified before implementation of any SET decision, if required. This document template will be provided in the sponsor's instruction manual and retained in the study master file and in the study center's files.

## 12. ADVERSE EVENT REPORTING

Timely, accurate, and complete reporting and analysis of safety information from clinical studies are crucial for the protection of subjects, investigators, and the sponsor, and are mandated by regulatory agencies worldwide. The sponsor has established Standard Operating Procedures in conformity with regulatory requirements worldwide to ensure appropriate reporting of safety information; all clinical studies conducted by the sponsor or its affiliates will be conducted in accordance with those procedures.

### 12.1. Definitions

#### 12.1.1. Adverse Event Definitions and Classifications

##### Adverse Event

An adverse event is any untoward medical occurrence in a clinical study subject administered a medicinal (investigational or non-investigational) product. An adverse event does not necessarily have a causal relationship with the treatment. An adverse event can therefore be any unfavorable and unintended sign (including an abnormal finding), symptom, or disease temporally associated with the use of a medicinal (investigational or non-investigational) product, whether or not related to that medicinal (investigational or non-investigational) product. (Definition per International Conference on Harmonisation [ICH])

This includes any occurrence that is new in onset or aggravated in severity or frequency from the baseline condition, or abnormal results of diagnostic procedures, including laboratory test abnormalities.

Note: The sponsor collects adverse events starting with the signing of the ICF (refer to Section 12.2.1, All Adverse Events, for time of last adverse event recording).

### **Serious Adverse Event**

A serious adverse event based on ICH and EU Guidelines on Pharmacovigilance for Medicinal Products for Human Use is any untoward medical occurrence that at any dose:

- Results in death
- Is life-threatening  
(The subject was at risk of death at the time of the event. It does not refer to an event that hypothetically might have caused death if it were more severe.)
- Requires inpatient hospitalization or prolongation of existing hospitalization
- Results in persistent or significant disability/incapacity
- Is a congenital anomaly/birth defect
- Is a suspected transmission of any infectious agent via a medicinal product
- Is Medically Important\*

\*Medical and scientific judgment should be exercised in deciding whether expedited reporting is also appropriate in other situations, such as important medical events that may not be immediately life threatening or result in death or hospitalization but may jeopardize the subject or may require intervention to prevent one of the other outcomes listed in the definition above. These should usually be considered serious.

If a serious and unexpected adverse event occurs for which there is evidence suggesting a causal relationship between the study drug and the event (eg, death from anaphylaxis), the event must be reported as a serious and unexpected suspected adverse reaction even if it is a component of the study endpoint (eg, all-cause mortality).

### **Unlisted (Unexpected) Adverse Event/Reference Safety Information**

An adverse event is considered unlisted if the nature or severity is not consistent with the applicable product reference safety information. For DACOGEN, the expectedness of an adverse event will be determined by whether or not it is listed in the Investigator's Brochure. For cytarabine, with a marketing authorization, the expectedness of an adverse event will be determined by whether or not it is listed in the SmPC.

### **Adverse Event Associated With the Use of the Drug**

An adverse event is considered associated with the use of the drug if the attribution is possible, probable, or very likely by the definitions listed in Section 12.1.2.

#### **12.1.2. Attribution Definitions**

##### **Not Related**

An adverse event that is not related to the use of the drug.

**Doubtful**

An adverse event for which an alternative explanation is more likely, eg, concomitant drug(s), concomitant disease(s), or the relationship in time suggests that a causal relationship is unlikely.

**Possible**

An adverse event that might be due to the use of the drug. An alternative explanation, eg, concomitant drug(s), concomitant disease(s), is inconclusive. The relationship in time is reasonable; therefore, the causal relationship cannot be excluded.

**Probable**

An adverse event that might be due to the use of the drug. The relationship in time is suggestive (eg, confirmed by dechallenge). An alternative explanation is less likely, eg, concomitant drug(s), concomitant disease(s).

**Very Likely**

An adverse event that is listed as a possible adverse reaction and cannot be reasonably explained by an alternative explanation, eg, concomitant drug(s), concomitant disease(s). The relationship in time is very suggestive (eg, it is confirmed by dechallenge and rechallenge).

**12.1.3. Severity Criteria**

An assessment of severity grade will be made using the National Cancer Institute Common Terminology Criteria for Adverse Events (NCI-CTCAE) version 4.0. Special Reporting Situations

Safety events of interest on a sponsor study drug that may require expedited reporting and/or safety evaluation include, but are not limited to:

- Overdose of a sponsor study drug
- Suspected abuse/misuse of a sponsor study drug
- Inadvertent or accidental exposure to a sponsor study drug
- Any failure of expected pharmacologic action (ie, lack of effect) of a sponsor study drug
- Unexpected therapeutic or clinical benefit from use of a sponsor study drug
- Medication error involving a sponsor product (with or without subject/patient exposure to the sponsor study drug, eg, name confusion)

Special reporting situations should be recorded in the eCRF. Any special reporting situation that meets the criteria of a serious adverse event should be recorded on the serious adverse event page of the eCRF.

**12.2. Procedures****12.2.1. All Adverse Events**

All adverse events and special reporting situations, whether serious or non-serious, will be reported from the time a signed and dated ICF is obtained until 30 days after the last dose of study drug. Serious adverse events, including those spontaneously reported to the investigator

within 30 days after the last dose of study drug, must be reported using the Serious Adverse Event Form. The sponsor will evaluate any safety information that is spontaneously reported by an investigator beyond the time frame specified in the protocol.

All events that meet the definition of a serious adverse event will be reported as serious adverse events, regardless of whether they are protocol-specific assessments.

All adverse events, regardless of seriousness, severity, or presumed relationship to study drug, must be recorded using medical terminology in the source document and the eCRF. Whenever possible, diagnoses should be given when signs and symptoms are due to a common etiology (eg, cough, runny nose, sneezing, sore throat, and head congestion should be reported as "upper respiratory infection"). Investigators must record in the eCRF their opinion concerning the relationship of the adverse event to study therapy. All measures required for adverse event management must be recorded in the source document and reported according to sponsor instructions.

The sponsor assumes responsibility for appropriate reporting of adverse events to the regulatory authorities. The sponsor will also report to the investigator (and the head of the investigational institute where required) all serious adverse events that are unlisted (unexpected) and associated with the use of the study drug. The investigator (or sponsor where required) must report these events to the appropriate Independent Ethics Committee/Institutional Review Board (IEC/IRB) that approved the protocol unless otherwise required and documented by the IEC/IRB.

An adverse event is any untoward medical occurrence in a clinical study subject administered a medicinal (investigational or non-investigational) product. An adverse event does not necessarily have a causal relationship with the treatment. An adverse event can therefore be any unfavorable and unintended sign (including an abnormal finding), symptom, or disease temporally associated with the use of a medicinal (investigational or non-investigational) product, whether or not related to that medicinal (investigational or non-investigational) product. (Definition per International Conference on Harmonisation [ICH])

This includes any occurrence that is new in onset or aggravated in severity or frequency from the baseline condition, or abnormal results of diagnostic procedures, including laboratory test abnormalities.

Note: The sponsor collects adverse events starting with the signing of the ICF (refer to Section 12.2.1, All Adverse Events, for time of last adverse event recording).

